Decitabine in combination with chidamide, cytarabine and homoharringtonine (DCHA) as postremission therapy for acute myeloid leukemia with t(8;21) :A multicenter prospective study

Sponsor: Chinese PLA General Hospital

NCT ID not yet assigned

Document Date: February 16, 2018

Purpose

Acute myelocytic leukemia (AML) is a highly heterogeneous group of malignant hematopathy. Chromosomal translocation with t (8; 21) (q22; q22), about 10 ~ 15% incidence in AML and 40% incidence in the AML-M2 type of leukemia, is a karyotype that is considered to have a good prognosis. The NCCN guidelines recommend that high-dose Ara-c regimens may benefit for patients, but with 30 to 40% relapse and serious risks on myelosuppression, infection and bleeding in high-dose Ara-c consolidation chemotherapy and more than 70% recurrence rate with KIT mutation. So the exploration of a relatively safe and efficient consolidation therapy is one of the difficult problems to be solved in the treatment of mitigatory t (8; 21) AML. We will investigate the safety and efficacy of a combination regimen including decitabine, chidamide, cytarabine and homoharringtonine as the postremission therapy for AML with t(8;21).

Primary Outcome Measure:

Progression free survival [Time Frame: 2 years]

Secondary Outcome Measures:

Overall survival [Time Frame: 2 years]

Estimated Enrollment: 120

Study Start Date: January 1, 2017

Estimated Study Completion Date: December 31, 2019

Estimated Primary Completion Date: December 31, 2018

Eligibility

Ages Eligible for Study: 14 Years to 65 Years

Sexes Eligible for Study: All

Gender Based: No

Inclusion Criteria:

Written informed consent provided.

The patients were diagnosed AML-M2 with t(8;21) (q22;q22) chromosomal changes and positive AML1-ETO fusion gene according to the 2008 World Health Organization (WHO) diagnostic criteria for malignant myeloid diseases.

Males or females aged ≥ 18 years, < 65 years.

ECOG performance status 0-3.

Life expectancy ≥ 3 months.

The morphology was Complete remission (CR) or Cri after 2 cycles of anthracycline induced chemotherapy.

No serious disease with heart, lung, liver and kidney.

The ability to understand and be willing to sign the Informed Consent Form of the experiment.

Patient who can start the investigational therapy within 3–6 weeks after the complete resection

Adequate liver function: Total bilirubin ≤ 1.5 x upper limit of normal (ULN), Aspartate aminotransferase (AST), alanine aminotransferase (ALT) ≤ 2.5 x ULN in subjects without liver metastases; ≤ 5 x ULN in subjects with liver metastases.

Adequate renal function: Serum creatinine ≤ 1.25 x ULN, or ≥ 60 ml/min.

Female subjects should not be pregnant or breast-feeding.

Exclusion Criteria:

Known allergic to prior treatment with drugs contained by the trial programme or with a chemical structure similar medicine.

Pregnancy, breast-feeding women and childbearing age patients who do not want to take contraceptive measures.

Active serious infection.

Patients with extramedullary lesions.

Patients who use drugs or drink alcohol for a long time to influence the evaluation of results.

Patients with mental illness or other conditions are unable to obtain knowledge and consent, and can not cooperate with the requirements of the completion of the test treatment and examination steps.

Patients with a history of the clinical significance of QTc prolongation (male $> 450\text{ms}$, female $>470\text{ms}$), ventricular tachycardia (VT), atrial fibrillation (AF), degree of heart block, muscle infarction (MI) within 1 years, congestive heart failure (CHF), with symptoms and drug therapy in patients with coronary heart disease.

Patients with abnormal liver function (total bilirubin $> 1.5 \times \text{ULN}$, ALT/AST $> 2.5 \times \text{ULN}$, or liver invasion ALT/AST $> 5 \times \text{ULN}$), renal function abnormality (serum creatinine $> 1.5 \times \text{ULN}$).

The researchers decided that patient was not appropriate to take part in the experiment.

Treatment regimen

HA:

homoharringtonine 2mg IV d1-5

cytarabine(Ara-C) 1500mg/m²(<60 year old) ;

1000mg/m²(>60 year old)

IV q12h d1,3,5

DCHA:

Decitabine 20mg/m² d8-12

Chidamide 30mg twice/week P.O. for two weeks per cycle

(four doses totally)

[figure not shown]
cytarabine(Ara-C) 1500mg/m²(<60 year old) ;

1000mg/m²(>60 year old)

IV q12h d1,3,5

homoharringtonine 2mg IV d10-14

Process schedule

Statistical analysis

SAS 9.0 software (SAS Institute) will be used in all statistical

analysis. Survival data were analyzed by the log-rank test, and survival curves will be plotted with the Kaplan-Meier method. t test will be used to assess the probability of significant differences of survival time. $P < 0.05$ was considered statistically significant.

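### Low-weight improvement: the readable plan makes DCHA safety an aim in patients already in remission, but sets no interim count of treatment-related deaths and no pause trigger

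*Combined protocol and SAP*

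**What the plan says.** The title describes "A multicenter prospective study". The Purpose section motivates the trial by "serious risks on myelosuppression, infection and bleeding in high-dose Ara-c consolidation chemotherapy" and continues: "So the exploration of a relatively safe and efficient consolidation therapy is one of the difficult problems to be solved". It then makes safety an aim: "We will investigate the safety and efficacy of a combination regimen including decitabine, chidamide, cytarabine and homoharringtonine as the postremission therapy".

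The Inclusion Criteria require remission ("The morphology was Complete remission (CR) or Cri after 2 cycles of anthracycline induced chemotherapy") and allow "ECOG performance status 0-3". Planned size is given as "Estimated Enrollment: 120". The primary outcome is 2-year progression-free survival, and the only secondary outcome is "Overall survival [Time Frame: 2 years".

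Under Treatment regimen, HA is cytarabine plus homoharringtonine. DCHA lists both at the same doses, with homoharringtonine on later days, and adds decitabine and chidamide. The Statistical analysis section covers software, the log-rank test, Kaplan-Meier curves, a t test and the 5% significance level, and nothing else.

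**The concern.** Patients in remission have something to lose from a toxic consolidation, and the sponsor's own rationale is that existing consolidation is hazardous. Followed as written, the readable plan contains no point during enrolment at which deaths on DCHA are added up across centres. It names no event that would count, no role that would count it and no number that would lead to a pause.

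This is separate from the lack of a listed toxicity outcome, because an adverse-event table at the end of the trial cannot act while patients are being enrolled. At stake is continued enrolment onto a regimen whose death rate is well above what the clinicians would accept. The documents give no rate, so the size of that risk can only be shown under assumptions.

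**Working it through.** **1. Text check.** The plan has no safety boundary to reproduce, and 120 comes without an effect size, power or allocation. The organ-function, cardiac/QTc and infection criteria apply at entry, and the lower cytarabine dose in older patients is set by age. None of them counts events on study.

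**2. Timing.** Study start (1 January 2017) to document date (16 February 2018) is 411 days. Start to estimated primary completion (31 December 2018) is 729 days. 411/729 = 0.564. Assume 60 of the 120 receive DCHA and accrual is uniform to that date: 0.564 × 60 = 33.8, so about 34 are already treated. Other reading: if every patient has 2 years of follow-up by study completion (31 December 2019), enrolment ended by 31 December 2017, 47 days before the document date.

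**3. Boundary.** For an acceptable rate r, use prior Beta(2r, 2(1−r)). Pause at the smallest count k ≥ 2 with P(rate > r | k of n) > 0.95. Example with r = 5%, n = 34: k = 4 gives Beta(4.1, 31.9) and probability 0.914; k = 5 gives Beta(5.1, 30.9) and 0.975. The boundary is therefore 5. At 44 and 54 it is 6 and 7.

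**4. Chance of a pause** (exact binomial recursion, looks at 34, 44, 54, complete outcomes, r = 5%): 0.038, 0.372, 0.772 and 0.951 at true rates of 5, 10, 15 and 20%.

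**5. Deaths avoided at a true 15%.** With no rule and no ad hoc stop: 60 × 0.15 = 9.0 deaths. The three looks stop with probability 0.592, 0.109 and 0.071. Mean exposure with no reporting lag = 34(0.592) + 44(0.109) + 54(0.071) + 60(0.228) = 42.4. Avoided = (60 − 42.4) × 0.15 = 2.6.

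The cycle number is not readable, so the lag until a patient is evaluable is unknown. With 34 treated, first look at 34 minus the lag, then every 10:

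| Lag (patients) | Mean exposure at 15% | Avoided at 15% (of 9.0) | Avoided at 10% (of 6.0) |
|---|---|---|---|
| 0 | 42.4 | 2.64 | 0.79 |
| 5 | 43.6 | 2.46 | 0.76 |
| 10 | 44.4 | 2.34 | 0.72 |
| 15 | 47.7 | 1.84 | 0.52 |
| 20 | 47.2 | 1.92 | 0.61 |
| 24 | 51.3 | 1.31 | 0.36 |

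Ten patients is 10 × 729/60, about 122 days. Patients not given DCHA still receive some consolidation. If its death rate is 5%, the net gain at 15% is (60 − 51.3) × 0.10 = 0.9 to (60 − 42.4) × 0.10 = 1.8.

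**6. Dependence on r.** On looks 34/44/54, r = 3%, 8% or 10% detects a true 15% with probability 0.943, 0.517 or 0.352. For r = 10% (boundaries 7, 9, 10), mean exposure is 52.7 with no lag, so (60 − 52.7) × 0.15 = 1.1 avoided; with a 10-patient lag after each look it is 0.6. The same two settings with r = 5% give 2.6 and (60 − 49.9) × 0.15 = 1.5.

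**7. Unnecessary pause at a true 5%, r = 5%.** Complete outcomes, 60 on DCHA: 0.038 (looks 34/44/54), 0.050 (24/34/44/54), 0.067 (every 10 from the start). With all 120 on DCHA and looks every 10: 0.107. A flat Beta(1,1) prior raises 0.038 to 0.114. If deaths enter before survivors complete the window, 100,000 simulated trials (accrual to day 729) give 0.067, 0.077, 0.100 and 0.151 for windows of 61, 122, 183 and 274 days.

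**8. What one centre sees.** If a centre treats 10 DCHA patients (assumed), P(at most one death) = (1−p)^10 + 10p(1−p)^9: 0.914 at p = 5% and 0.544 at p = 15%.

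**The case against.** Four points can be made against acting, and each has some force.

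- A reader might infer that the trial runs without safety oversight. The documents do not support that. The DCHA figure is not shown, nothing readable follows the Process schedule heading, and this is a short summary. A safety check could sit there or in other documents, and investigators or an ethics committee could stop ad hoc. What stands is that the Statistical analysis section, which reads as complete, has no such rule.
- A reader might take 1.3 to 2.6 deaths avoided as the expected benefit. That range needs r = 5%, a true 15%, 60 on DCHA and accrual running to the primary completion date. That date is not stated to be the end of enrolment, and recruiting up to it would leave late entrants little follow-up for a 2-year outcome. The 2-year frame may be only an estimation horizon, so closed accrual is possible but not established.
- The single-centre calculation assumes that each centre sees only its own deaths. The documents do not say how deaths are shared, so it illustrates why pooling helps and shows no failing.
- The Bayesian form, the 0.95 threshold, the prior and the spacing of 10 are choices. Other rules would serve, and a pooled count without a boundary is an acceptable minimum.

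Nor do the documents show that DCHA is more toxic than HA; they give no toxicity rates.

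**Conclusion.** The gap in the readable text is real, and closing it is a cheap improvement of low weight. The benefit has to be stated conditionally. With 60 on DCHA, uniform accrual to 31 December 2018 and a true 15%, about 1.3 to 2.6 of 9.0 deaths are avoided at r = 5%, and about 0.6 to 1.1 at r = 10% (looks 34/44/54, lag 10 or 0). At a true 10% with r = 5% it is about 0.4 to 0.8 of 6.0. If accrual had closed, halting enrolment avoids none, and the rule can only prompt review of the cycles still to be given. All of these rest on assumed inputs. They apply to a rule with complete outcomes and were not computed for one that counts deaths early. The rule guards against a gross excess, not a small one.

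**What to change.** Add to the Statistical analysis section:

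- **Who and what.** The sponsor's coordinating investigator counts treatment-related deaths in remission, pooled over centres, from first DCHA dose to 30 days after the last DCHA cycle. Centres report each death in remission when it occurs.
- **When.** At once, then after every 10 further evaluable DCHA patients; enrolment continues between counts.
- **Denominator.** Patients whose window is complete. A patient who dies enters on the date when the planned window would have ended. If deaths are to count sooner, re-check the boundary by simulation before printing it.
- **Action.** Reaching the boundary pauses DCHA enrolment for review or, if accrual has closed, prompts review of remaining DCHA cycles. It does not terminate the trial.
- **Boundary.** The clinicians choose r, and the protocol prints the prior and the table. For r = 5% with complete outcomes: 3 deaths at 10–17 evaluable patients, 4 at 18–28, 5 at 29–40, 6 at 41–53, 7 at 54–67. If more than 67 may receive DCHA, extend the table.

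Minimum version: the named role and the pooled count every 10 evaluable patients, without a boundary.

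Cost: one paragraph, one table and a short amendment. Deaths are already needed for overall survival, but each death in remission must be attributed. The main downside is an unnecessary pause: about 0.04 to 0.07 at a true 5% for 60 DCHA patients with complete outcomes, and up to about 0.15 if deaths count early with a nine-month window.

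### The stated primary completion date falls 729 days after study start, so an analysis then cannot estimate PFS at 24 months from enrolment

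*Combined protocol and SAP*

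**What the plan says.** The outcome and date entries at the start of the combined protocol and SAP give:

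- Primary outcome: "Progression free survival [Time Frame: 2 years", with the bracket then closed.
- Secondary outcome: "Overall survival [Time Frame: 2 years", likewise.
- Start: "Study Start Date: January 1, 2017".
- Primary completion: "Estimated Primary Completion Date: December 31, 2018".
- End of study: "Estimated Study Completion Date: December 31, 2019".
- Size: "Estimated Enrollment: 120".

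The Statistical analysis section names Kaplan-Meier curves and the log-rank test for survival data, and also a t test on survival time. It ties none of these to a date.

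The readable text gives no accrual period, PFS time origin, minimum follow-up or data cut-off rule. It does not say whether 2 years is a landmark at which PFS is estimated or the longest period over which a patient is observed. One figure in the treatment section is not visible, and nothing is readable under the heading "Process schedule". Some of these details may be there, but neither item could alter the interval between the printed dates.

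**The concern.** A primary completion date is normally when the last data for the primary outcome are in hand. Here the span from study start to that date is the same length as the follow-up that the primary outcome names. Enrolling 120 patients takes time, and each day of it comes off the follow-up of patients who enter later.

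If the sponsor analyses at the stated date and reports 2-year PFS, the Kaplan-Meier curve will have essentially nobody at risk at the point being quoted. The estimate would not exist or would be an extrapolation. A comparison of regimens would also rest on fewer events than full follow-up would give.

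Overall survival carries the same 2-year time frame. The plan does not tie it to the primary completion date, so it is affected only if it is analysed then.

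**Working it through.** **Exact part: calendar days from the printed dates**

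- 1 Jan 2017 to 31 Dec 2018: 729 days, or 729 / 30.4375 = 23.95 months.
- Two calendar years from 1 Jan 2017 end on 1 Jan 2019: 730 days.
- 31 Dec 2018 to 31 Dec 2019: 365 days.
- 31 Dec 2017 to 31 Dec 2019: 730 days, so anyone enrolled by 31 Dec 2017 can reach 24 months by the study completion date.

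A first-day patient is one day short of 2 years at primary completion. That day is trivial. What matters is that a patient enrolled *e* days after the start has at most 729 − *e* days of follow-up. With PFS from enrolment, the number at risk at 24 months is zero whatever the event rate or accrual pattern.

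The plan gives no power, event target or sample-size derivation, so it has no figure of its own to reproduce.

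**Illustration: size of the loss (assumed inputs)**

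Only the 120 patients and the dates come from the plan. The following are assumed:

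- a 35% 2-year event rate with constant hazard;
- uniform accrual over *A* = 12, 18 or 24 months from 1 Jan 2017;
- PFS from enrolment, with no dropout.

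The plan's Purpose section mentions 30 to 40% relapse. That figure has no time point and is not PFS, so it does not supply the rate.

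Formulas, with *T* = 24 months (31 Dec 2018) or 36 months (31 Dec 2019):

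- Hazard: λ = −ln(0.65)/24 = 0.01795 per month.
- Expected events within 24 months of entry: 120 × mean over entry *e* of [1 − exp(−λ·min(*T* − *e*, 24))].
- At risk at *t* months: 120 × [min(*A*, *T* − *t*)/*A*] × exp(−λ*t*).

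Worked case, *A* = 24 and *T* = 24: the mean survival term is (1 − 0.65)/(0.01795 × 24) = 0.8125, so events = 120 × 0.1875 = 22.5. Full 2-year follow-up of all patients gives 120 × 0.35 = 42, so the shortfall is 19.5/42 = 46.4%.

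| Accrual | Events, 31 Dec 2018 | Below 42 | At risk at 24 mo | Events, 31 Dec 2019 | Below 42 | At risk at 24 mo |
|---|---|---|---|---|---|---|
| 12 mo | 33.0 | 21.5% | 0 | 42.0 | 0% | 78 |
| 18 mo | 27.9 | 33.5% | 0 | 40.5 | 3.5% | 52 |
| 24 mo | 22.5 | 46.4% | 0 | 37.5 | 10.8% | 39 |

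Precision of 24-month PFS at 31 Dec 2019, for accrual over 12, 18 or 24 months:

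- Greenwood standard error: 4.35, 4.49 or 4.82 points.
- Pooled 95% half-width (× 1.96): 8.5, 8.8 or 9.4 points.
- Per regimen (× √2): about 12.1, 12.5 or 13.3 points. This assumes HA and DCHA are two arms of 60 with the same PFS; the readable text does not state allocation.

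**Sensitivity to the event rate**

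| Rate | Events, 31 Dec 2018 | Events, 31 Dec 2019 | Pooled half-width, 31 Dec 2019 |
|---|---|---|---|
| 30% | 28.0, 23.7, 19.1 | 36.0, 34.7, 32.0 | 8.2, 8.5, 9.0 |
| 40% | 38.0, 32.3, 26.0 | 48.0, 46.4, 43.0 | 8.8, 9.1, 9.7 |

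The pattern is the same: about 21% to 47% of events are lost at the earlier date, and 0% to 11% at the later one.

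**The case against.** The strongest reply is that the conflict depends on things the plan does not say: that PFS runs from enrolment, that 2 years is a landmark, and that the primary analysis is done on the primary completion date. A 2-year time frame can also mean observation for up to 2 years. Kaplan-Meier and log-rank handle administrative censoring, and the plan promises no 24-month point estimate. This is fair. On the maximum-window reading the dates are compatible, but the result is PFS over shorter, variable follow-up and should not be called 2-year PFS. The text needs settling on either reading.

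An earlier origin, such as remission or diagnosis, would add each patient's pre-enrolment interval. It would take some early entrants past 24 months, but few unless that interval is long.

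Much information would still exist at 31 December 2018. On the 35% assumption, about 97, 64 or 48 patients would be at risk at 12 months under 12-, 18- or 24-month accrual. That stands: the gap is in late follow-up.

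The statement that the loss is not bias applies to Kaplan-Meier and log-rank only. The planned t test on survival time ignores censoring. That is a separate defect, which an early cut-off would make worse.

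Moving the date does not fully cure late accrual. If enrolment took 24 months, only about half the patients could have 24 months of follow-up by 31 December 2019. A 24-month estimate would still be possible, with about 39 at risk on the 35% assumption.

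**Conclusion.** The concern holds. With PFS from enrolment, an analysis at the stated primary completion date cannot provide a 24-month estimate, because 729 days leave no room for accrual plus 2 years of follow-up. That conclusion rests on the printed dates and the enrolment origin alone.

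The size of the event loss, roughly a fifth to just under a half, rests on the assumed event rate, constant hazard and uniform accrual, and is illustrative. Accrual status on the document date is unknown and plays no part.

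This should be fixed. It limits what the primary outcome can support, but it does not invalidate the Kaplan-Meier or log-rank analysis.

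**What to change.** 1. State the PFS time origin and the data cut-off, and say whether 2 years is a 24-month landmark or a maximum observation window.
2. Move the primary completion date and the primary PFS analysis to the existing study completion date, 31 December 2019.
3. Report the 24-month Kaplan-Meier estimate with its confidence interval and numbers at risk, by regimen if the regimens are compared.
4. If accrual closed after 31 December 2017, state the actual minimum follow-up at that cut-off. Waiting until 24 months after the last enrolment is optional.
5. If 31 December 2018 is kept, describe the result as PFS to that cut-off, not as 2-year PFS.

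Moving the date costs a primary read-out 365 days later, within the study's existing end date, with no extra patients and no change of outcome. Keeping the date costs only a change of wording, but gives up the 24-month estimate.

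### The plan for 2-year PFS and OS gives a P-value verdict and plotted curves, but no hazard ratio, 2-year estimate, difference or confidence interval

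*Combined protocol and SAP*

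**What the plan says.** The outcome sections name "Progression free survival [Time Frame: 2 years]" as primary, with 2-year overall survival as secondary, and "Estimated Enrollment: 120". The Purpose section sets out to study the safety and efficacy of the DCHA combination.

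Apart from naming the software, the Statistical analysis section has three elements:

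- A test and a plot: "Survival data were analyzed by the log-rank test, and survival curves will be plotted with the Kaplan-Meier method".
- A further comparison, made on the times themselves: "t test will be used to assess the probability of significant differences of survival time".
- A threshold for the verdict: P below 0.05 "was considered statistically significant". Sidedness is not given.

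This paragraph shows no sign of redaction or a gap. It mentions no hazard ratio, regression model, 2-year survival estimate, between-group difference or confidence interval, and it gives no target effect, power or event count. Treatment regimen lists HA and DCHA. The readable text does not say how they are allocated or compared. A figure is missing from this part of the document and may show it.

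**The concern.** A log-rank test yields a P-value, not a size of effect. Kaplan-Meier curves are to be plotted, but no estimate at 2 years and no interval is to be reported from them. The t test compares mean survival times as if every time were observed, which is not so when most patients are event-free at the end of follow-up. The only usable inference left is whether the log-rank P falls below 0.05.

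At stake is what the trial can conclude about its own primary outcome. A non-significant P could come from no effect or from a large benefit imprecisely measured, and the planned output would not separate the two. A significant P would carry no stated magnitude. The same applies to OS.

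**Working it through.** **No planned figure to reproduce.** The enrollment of 120 comes with no effect size, power or event count.

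**Inputs from the documents.** N = 120; 2-year PFS; threshold 0.05; and, from Purpose, "30 to 40% relapse" after high-dose cytarabine.

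**Assumptions, not in the documents.** HA v DCHA at 60:60; the 30-40% figure used as the 2-year PFS event rate on HA (the protocol gives it as relapse, with no time point, and not for HA); proportional hazards; two-sided test; 24 months complete for everyone; true hazard ratio (HR) 0.5 as an example of a large benefit.

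**Formulas.**
- DCHA event probability: p1 = 1 − (1 − p0)^HR
- Events: D = 60·p0 + 60·p1
- Largest observed HR giving P < 0.05: exp(−1.96 × 2/√D)
- Power: Φ(|ln HR|·√D/2 − 1.96)
- 95% interval for the HR: estimate divided and multiplied by exp(1.96 × 2/√D)

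**Worked line, p0 = 0.35, HR 0.5.** p1 = 1 − 0.65^0.5 = 0.194. D = 21.0 + 11.6 = 32.6. Critical HR = exp(−3.92/5.71) = 0.503. Power = Φ(0.693 × 5.71/2 − 1.96) = Φ(0.02) = 0.508.

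| HA rate | DCHA rate | Events | Critical HR | Chance of P ≥ 0.05, formula | Simulated log-rank (5,000; 20,000 runs) |
|---|---|---|---|---|---|
| 30% | 16.3% | 27.8 | 0.48 | 55.3% | 55.9%; 57.1% |
| 35% | 19.4% | 32.6 | 0.50 | 49.2% | 51.4%; 50.9% |
| 40% | 22.5% | 37.5 | 0.53 | 43.5% | 44.4%; 45.1% |

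**Sensitivity of the chance of P ≥ 0.05.**
- True HR 0.4: 22-37%. True HR 0.6: 64-72%.
- HR 0.5 with one third of patients on HA: 52-63%.
- HR 0.5 analysed at the stated primary completion date (December 31, 2018, two years after study start), with accrual uniform over 1-2 years: about 15-29 events and 53-74%.
- HR 0.5 with a 70% event rate in every HA patient (Purpose gives more than 70% recurrence with KIT mutation): 18%.

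**What an interval would add.** With 33 events the interval factor is exp(3.92/√33) = 1.98.

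| Observed HR | Planned report | 95% interval the plan omits |
|---|---|---|
| 1.00 | not significant | 0.51 to 1.98 |
| 0.55 | not significant | 0.28 to 1.09 |
| 0.50 | significant | 0.25 to 0.99 |

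The first two rows get the same verdict but mean different things: the second leaves open a more than threefold reduction in hazard (1/0.28 = 3.6). The third is significant, yet compatible with almost no effect. On the 2-year scale, at HR 0.5, the differences are 13.7 ± 14.9, 15.6 ± 15.7 and 17.5 ± 16.3 points for HA rates of 30%, 35% and 40%, using half-width 1.96·√[p0(1 − p0)/60 + p1(1 − p1)/60].

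**The t test.** With 28-38 events among 120 patients, 82-92 patients (about 69-77%) would have no observed event time. A comparison of mean times does not account for that.

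**The case against.** The strongest objection is that the chance of missing a real benefit belongs to the number of events, not to the choice of what to report. A reader might infer that the plan would call a large benefit not significant about half the time because it omits a hazard ratio and interval. The documents do not support that link: adding estimates leaves the power where it was. Nor is about half a property of this trial. It needs two compared groups of 60, a hazard ratio near 0.5, and a relapse figure with no time point read as a 2-year HA rate. Complete 24-month follow-up also does not fit the stated primary completion date, by which only patients enrolled at the very start could have it. This part of the objection stands, so the power figures serve here only as a conditional illustration.

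A reader might also infer that non-significance is the likely outcome unless the hazard is more than halved. At a 40% HA rate and HR exactly 0.5, significance is slightly the likelier outcome (56.5% by formula), so that is too strong.

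It is also fair that a 2-year point estimate can be read off a plotted Kaplan-Meier curve. What the plan still lacks is a reported estimate, its interval and the comparison. Finally, the readable text describes no randomisation. If the groups are not randomised, a hazard ratio with an interval expresses sampling error but not confounding. That is a caveat the fix must carry; it does not justify reporting no estimate.

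**Conclusion.** The concern holds as an omission: no effect estimate or confidence interval is planned for PFS or OS, and the t test on survival time does not fill the gap. This rests on the text alone and is true whatever the power, and whether there are two groups or one. With a single group the log-rank test has nothing to compare, and a 2-year estimate with an interval is the only informative result.

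The size is conditional. Under the assumptions listed above there would be about 28-38 events at HR 0.5, P < 0.05 would need an observed HR of about 0.48-0.53 or lower, and a true HR of 0.5 would be called not significant about 43-57% of the time. The sensitivity cases move this well outside that range in both directions. These figures show why a bare verdict would say little here; they do not establish the trial's actual power.

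**What to change.** Amend Statistical analysis as follows:

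1. Make the primary result the PFS hazard ratio, DCHA v HA, with 95% CI, from a Cox model adjusted for a short pre-specified list of baseline factors: age, and CR v CRi and KIT status if these are recorded. Eligibility requires CR or CRi but does not say that the two are recorded separately.
2. Report Kaplan-Meier 2-year PFS in each group with 95% CI (Greenwood variance, log-log scale), and the between-group difference with 95% CI.
3. Do the same for OS.
4. Keep the two-sided log-rank P as supporting evidence, drop the t test on survival time, and state that P ≥ 0.05 will not be read as no difference.
5. If the groups are not randomised, state that the interval does not cover confounding.
6. If there is only one treated group, make 2-year PFS with 95% CI the primary result and drop the log-rank test.

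The cost is a few sentences in the SAP and routine additional analyses; no extra patients or visits are needed. The downside is that a wide interval will be visible in the report. The change does not raise power.

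### A t test on survival time ignores censoring and adds an unranked second test of PFS and OS beside the log-rank test

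*Combined protocol and SAP*

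**What the plan says.** The primary outcome is given as "Progression free survival [Time Frame: 2 years" and the secondary as "Overall survival [Time Frame: 2 years", both closing with a bracket. Both are time-to-event outcomes.

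The Statistical analysis section states: "Survival data were analyzed by the log-rank test, and survival curves will be plotted with the Kaplan-Meier method". The next sentence says that a "t test will be used to assess the probability of significant differences of survival time". A significance threshold of P below 0.05 follows, without a stated side and without a split or ranking between the two tests.

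No sentence restricts the t test to fully observed variables, makes it descriptive, gives a censoring rule, or says which test decides the PFS comparison.

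The first page of the protocol gives "Estimated Enrollment: 120" and "Study Start Date: January 1, 2017", with primary completion on 31 December 2018 (month 24) and study completion on 31 December 2019 (month 36). The Purpose section cites "30 to 40% relapse" after high-dose cytarabine consolidation.

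**The concern.** A t test needs a known time for every patient. For a patient who is still event-free at the data cut, only a lower bound on the survival time is known. The analyst then has two options:

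- Enter the censored time as if it were the survival time. The test then compares a mixture of survival and length of follow-up, and the follow-up part depends on when each group was enrolled.
- Keep only patients with an event. This discards most of the sample and selects patients on the outcome under study.

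Neither option estimates a difference in survival. The sentence also creates a second test of a comparison that the log-rank test already covers. The two can disagree, and the plan does not say which would count. A t-test p-value below 0.05 on PFS could therefore be reported as evidence of benefit when it reflects only calendar time, or when the log-rank test is not significant.

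**Working it through.** The plan states no power, effect size or event target, so it has no figure of its own to reproduce. The check is by calculation and simulation.

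**Inputs from the documents.** Total 120 patients; 2-year outcomes; data cuts at month 24 (primary completion) and month 36 (study completion); alpha 0.05; background relapse of 30 to 40%.

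**Assumptions.** 60 patients per group, since the available text does not state the allocation; exponential PFS; uniform accrual; the background relapse figure read as a 2-year event rate, with 35% as the central value; a hazard ratio of 0.5 to illustrate power.

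**Step 1: how much is censored.** The hazard is -ln(0.65)/24 = 0.01795 per month, so the true mean PFS is 1/0.01795 = 56 months. If follow-up is uniform from a to b months, the expected event fraction is

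1 - (e^(-λa) - e^(-λb)) / (λ(b - a)),

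and the mean observed time is that fraction divided by λ.

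- Accrual over months 0-24, cut at 24 (follow-up 0-24): event fraction 0.188, or 22.5 events in 120. About 81% are censored and the mean observed time is 10.4 months.
- Same accrual, cut at 36 (follow-up 12-36): event fraction 0.345, or 41.4 events. About 66% are censored and the mean is 19.2 months.
- Accrual over months 0-12, cut at 36 (follow-up 24-36): event fraction 0.415 and mean 23.1 months.

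The mean that the t test would use is thus about 10 to 23 months, set by the calendar, against a true mean of 56.

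**Step 2: no treatment effect, different enrolment dates.** Suppose one group enrols over months 0-20 and the other over months 4-24, with a cut at month 36. Follow-up is 16-36 v 12-32 months. The same formula gives mean observed times of 20.6 and 18.0 months. That is a gap of 2.6 months between groups with identical survival.

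Simulated false-positive rates for the t test on all observed times:

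| Enrolment (months) | Cut | Truncated at 24 months | t test |
|---|---|---|---|
| 0-20 v 4-24 | 36 | no | about 37% |
| 0-20 v 4-24 | 36 | yes | about 20% |
| 0-12 v 3-15 | 36 | no | about 18% |
| 0-12 v 3-15 | 36 | yes | about 5% |
| 0-12 v 3-15 | 24 | no | about 61-62% |

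For the two untruncated month-36 rows, the log-rank test gave about 5%.

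A second set had HA enrolling over months 0-24 and DCHA starting 3, 6 or 12 months later but ending at the same time, with a cut at month 36. The t test on all times gave 9.3%, 22.9% and 80.3%. On event times only it gave 5.5%, 8.1% and 21.1%. The log-rank test gave 4.8% to 5.1%.

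**Step 3: no treatment effect, identical follow-up.** Over 2-year event rates of 30, 35 and 40% and three follow-up patterns, the t test on all times alone gave 4.6% to 5.5%, which is close to nominal. If significance on either test counts, the upper bound is 0.05 + 0.05 = 0.10, and independent tests would give 1 - 0.95² = 0.0975. Simulation gave 6.4% to 9.3% with the t test on all times and 9.3% to 10.1% with it on event times only. The log-rank test alone gave 4.5% to 5.6%.

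**Step 4: power at hazard ratio 0.5, 35% control event rate.**

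| Setting | Log-rank | t test, all times | t test, events only |
|---|---|---|---|
| Accrual 0-24, cut 24 | 28% | 9% | 5% |
| Accrual 0-24, cut 36 | 49% | 27% | 5% |
| Accrual 0-12, all followed 24 months, truncated there | 49% | 41% | 6% |
| HA 0-24, DCHA 6-24, cut 36 | 45% | 5% | 5% |

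In the last row DCHA has the better survival but the shorter follow-up. The two nearly cancel, and the t test on all times misses the effect.

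**The case against.** **The false-positive figures depend on the scenario.** The outcomes have a 2-year window. Truncating at 24 months lowers the 37% to about 20% and the 18% to about 5%. With identical follow-up the t test keeps its nominal error, and with complete 2-year follow-up its power loss is modest (41% v 49%). This stands, so the size should be read as a range. It does not clear the sentence. The plan states no truncation rule, and at its own month-24 primary completion date a 3-month shift gives about 61-62%.

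**Staggered enrolment is assumed.** The documents do not say that the groups enrol at different times. A figure beside the regimens is missing from the text available here, so the lack of an allocation statement proves nothing. This also stands: unequal follow-up is a risk, not an established fact.

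**No either-test rule is written.** The log-rank test is named first, and the plan never says that success may be claimed on either test. That is true. The defect is that no deciding test is named; 6 to 10% is what follows if either is accepted.

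**The event rate is soft.** The 30 to 40% has no time horizon and describes other treatment, and the same sentence gives more than 70% recurrence with KIT mutation. The censored share is therefore uncertain. That there is censoring is not: with a cut 24 months after study start, any event-free patient enrolled after the first day has less than 2 years of follow-up.

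**A valid test is already specified.** It is, and so the primary result can be rescued by deletion alone. That makes the repair cheap but does not make the sentence right.

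**Conclusion.** The concern holds. As written, the plan applies a method that cannot use censored observations to its primary and secondary outcomes, and sets it beside a valid test at the same threshold with no ranking.

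The harm takes two forms:

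- **Follow-up differs between groups.** The t test's p-values are unreliable. False-positive rates ran from about 5% to 62% for average enrolment shifts of 3 to 4 months, depending on data cut and truncation, and reached 80% in the most extreme pattern tried.
- **Follow-up is identical.** The t test alone is near 5%, but it loses power against the log-rank test, and accepting either test raises the error to about 6 to 10%.

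These sizes rest on the assumed 60 per group, exponential PFS, accrual patterns, event rate and hazard ratio. The conclusion that the t test does not belong here does not depend on them. Because the sentence governs the primary endpoint, it should be corrected before any comparison of outcomes.

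**What to change.** Delete the t-test sentence, or restrict it to continuous variables that are observed for every patient. State that PFS is compared by one two-sided log-rank test at 0.05 and that this test alone decides the primary comparison. Name the log-rank test for OS as the secondary comparison. State the censoring rules, including whether follow-up is truncated at 24 months.

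Optional additions are a Cox hazard ratio with 95% CI and Kaplan-Meier 2-year rates with 95% CI. If a difference in mean time is wanted, restricted mean survival time to 24 months allows for censoring, provided follow-up in both groups reaches that point.

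The cost is a few lines in the Statistical analysis section. No extra patients, data or follow-up are needed.
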